Cover Page

Official Title: Prospective Longitudinal Pilot Study on the Association between Treatment of Allergic Rhinitis and Cognitive Ability in Children

Date: 11 April 2018

Study Protocol and Statistical Analysis Plan

INTRODUCTION

Allergic rhinitis is the reportedly second most common reported chronic health condition in Hong Kong children under the age of 14, with the Child Health Survey 2005-2006 indicating a prevalence of 24.5% [1]. Allergic rhinitis is a type I hypersensitivity reaction, which occurs when IgE antibodies are produced against allergens, leading to the activation of mast cells which release inflammatory mediators. Common allergens in Hong Kong include house dust mite and cockroaches [2]. Allergic rhinitis causes a multitude of symptoms including itching, sneezing, nasal discharge, post-nasal drip, and nasal congestion. It can cause poor quality sleep, leading to daytime sleepiness, decreased cognitive ability, mood instability and fatigue. Allergic rhinitis leading to a reduction in quality of life in adults has been well established, leading to impediment of cognitive processes and poorer ability in attention-requiring activities (e.g. driving) [3]. These symptoms can similarly significantly impede a child's education and quality of life. It is estimated that up to 90% of allergic rhinitis patients are untreated, insufficiently treated, or inappropriately treated [4].

With regards to children and teenagers, some studies have suggested that allergic rhinitis can cause significant cognitive difficulties, with detrimental effects on children's education and examination performance[5], however others suggest there is no association[6]. A 2014 longitudinal cohort study on the treatment of allergic rhinitis in children showed an improvement in attention and divided attention after 1 year of treatment[7]. There are little studies regarding the effect of treatment of allergic rhinitis on cognitive abilities in children.

BRIEF SUMMARY OF STUDY

Pilot study on the association between allergic rhinitis and cognitive ability in children aged 11-14 within the same year group at school. Primary outcome measures include cognitive tests (Digit Span Test, Stroop Test, Chinese Auditory Verbal Learning Test, Verbal Fluency Test, and Trail Making Test), so as to assess the cognitive ability of allergic rhinitis patients before and after treatment compared to a control group. Rhinitis Symptom Utility Index (RSUI) of patients will be the secondary outcome measured through questionnaires. Positive skin prick test and endoscopy examination (taking place in Prince of Wales hospital) will be required before the diagnosis of allergic rhinitis. The data will be analyzed by the Multilevel models. Collectively, an estimate of 34 allergic rhinitis patients with 106 control samples are to be recruited in a secondary school. Written consent will be required prior to the study, and all participants have the right to withdraw from the study at anytime. Should any issues arise, subjects and their legal guardians may contact research staff [name] during office hours.

RESEARCH OBJECTIVES

1. To investigate, if any, the differences between normal and allergic rhinitis patients in terms of cognitive function
2. To investigate the impact of allergic rhinitis on different areas of cognitive function
3. To investigate the improvement of cognitive function in children after 8 weeks of standard treatment of allergic rhinitis

RESEARCH HYPOTHESIS

Children with allergic rhinitis are expected to have a heightened improvement in cognitive abilities after the treatment compared to the normal control group due to relief of their nasal symptoms.

STUDY DESIGN

This study is a prospective longitudinal pilot study to take place from 1 Dec 2017 to 31 Dec 2018. Final report will be completed 30 June 2019.

STUDY SAMPLE AND SETTING

The study is to be performed in Hong Kong, with subjects aged 11-14 studying Form 1 and 2 in secondary school being recruited. Recruitment and cognitive testing will take place at the secondary school, whilst physician follow up and skin prick tests will take place at Prince of Wales Hospital. Healthy individuals as well as patients with a history of allergic rhinitis will be recruited. Chinese will be the main language used. The total number of the Form 1 students within the school will be around 200. The estimated participation rate will be approximately 70%. As the prevalence of allergic rhinitis in Hong Kong children under the age of 14 is approximately 24.5%[1], the expected number of participants and students with allergic rhinitis are 140 and 34 respectively.

STUDY FUNDING

Study funding will be sourced from Department of Otorhinolaryngology, Head and Neck Surgery (ENT), Faculty of Medicine, The Chinese University of Hong Kong (CUHK).

ETHICAL CONSIDERATIONS

Ethical approval will be sought from The Joint Chinese University of Hong Kong - New Territories East Cluster Clinical Research Ethics Committee (CUHK-NTEC CREC). Legal guardians will be well-informed as to the nature of the study and if necessary, the medication treatment and possible side effects. Invitation letter (Appendix 1) will be sent and written consent (Appendix 2) will be obtained from willing participants in the study. Confidentiality of all personal data, including questionnaire responses, will be kept in accordance with the Hong Kong Privacy Ordinance. Names and other identifying information will be omitted from the electronic database. All computer records will be locked with a password. Subjects will be withdrawn from the study immediately if his/her legal guardian chooses to withdraw consent. Files will be locked in the cabinets and will only be assessed by authorized research staff.

PRECAUTIONS TO PROTECT SUBJECTS

As subjects are under the age of 18, the subjects and legal guardians will be fully informed of the nature, scope, and possible consequences of the study. This study presents no greater than minimal risk to children and their safety and welfare are of utmost importance. Legal guardians have the right to withdraw subjects from the program at any time. Standard treatment for allergic rhinitis will be prescribed by physician according to guidelines. If issues arise, research staff will be available for subjects to contact during office hours.

MATERIALS AND INVESTIGATIONS USED

Rhinitis Symptom Utility Index (RSUI)

The RSUI is a preference-weighted measure of common rhinitis-related symptoms presented in a 10-item questionnaire (Appendix 4). Five rhinitis-related symptoms (stuffy or blocked nose, runny nose, sneezing, itchy eyes, and itchy nose or throat) are assessed with a 4-point Likert scale in terms of their frequency and severity during the past 14-day period. Frequency of each symptom is judged as either “not at all”, “1-3 days”, “4-7 days”, or “8-14 days”. Severity of each symptom is evaluated as “not applicable”, “mild”, “moderate” or “severe”. RSUI is the utility of the symptom state on a scale where the best state (no symptoms) has a score of 1 and the worst possible state (severe symptoms for 8 to 14 days) has a score of 0. ^[8]

Digit Span Test (DST)

Digit Span Tests are commonly seen in the Wechsler tests for intelligence. The current version used is a modified version by Lee and King (2010) ^[9], with higher ceiling and simplified administration to Final Version (Dated on 11 April 2018)

prevent exhaustion. There are two parts of the test: forward span and backward span. Forward span serves to assess auditory sustained attention, whereas backward span tests for the participant's working memory. In the forward span test, participants listen to a series of number digits and repeats the sequence of numbers heard. The digit series will increase in length by 1 after each successful trial until the subject fails to repeat the series in its entirety. In the backward span test, the subject listens to a series of numbers, but repeats the numbers in reverse sequence. Alike the forward span test, the digit series will increase in length by 1 after each successful trial until the subject fails to recall the sequence in its entirety. The digit span test is a well-established test for the pediatric population, with multiple studies utilizing it as an assessment of working memory in children. ^[10]

Stroop Test (Chinese Translated Victoria Version)

To test selective attention, response inhibition and speed of information processing, the Victoria Stroop Test will be utilized. With the administration time of approximately 5 minutes, the Victoria Stroop Test is a shortened, psychometrically sound version of the original Stroop Colour-Word Test. Participants will be shown 3 cards in total, with his/her response time to each card being recorded. The first card will show dots of differing colours, with participants being asked to recite the colours shown. The second card contains a list of random words printed in different colours and the participant will be asked to name the colour of the words. The third and last card contains colour words printed in ink that is coloured different from the word, with the participant being asked to name the colour rather than read the word. The difference in the time required to respond to each of these colours allows the measurement of interference and hence the Stroop effect. The Stroop Colour and Word Test has previously been used to assess cognitive function in allergic rhinitis patients^[11] and also depressive patients^[12].

Chinese Auditory Verbal Learning Test

For assessment of verbal learning and memory domain, the Chinese Auditory Verbal Learning Test will be utilized. This test, based on the original Rey Auditory Verbal Learning Test, was developed by local researchers and psychologists, and has been used previously on Chinese adolescents^[9]. Participants are presented with a list of 15 words (List A), and are asked to read this list aloud 5 times, with each time being followed by a free recall. Following this, an interference list of 15 words (List B) will be presented to the participant. Participants will be asked to read aloud and recall the interference list (List B), and then to recall the words from List A without further presentation. After a 30 minute delay, the participants will once again be asked to recall the words from List A without regard to order. The number of words recalled will be used as a measurement of memory retrieval. Afterwards, a list of words will be presented to the participants and they will have to recognize those that originated from List A.

Verbal Fluency Test

Participants will be given a category and asked to list as many words as possible relating to the category (e.g. vegetables). The number of words spontaneously produced within 1 minute will be measured and used to assess one of the executive functions, semantic fluency. The Word Fluency Test has previously been used in multiple neuropsychological studies^[13] and also as a tool for measuring executive functions in children ^[14].

Trail Making Test

Participants will be given two sheets and asked to draw a line to connect the circled numbers from smallest to largest numerically in Part A, and draw a line to connect first a circled number and then a circled alphabet in numerical and alphabetical way alternatively. The test will take 5 to 10 minutes and be used to assess one of the executive functions, selective attention. The Trail Making Test has previously been used in psychometric studies[21] and also as a tool for measuring executive functions in children.

Skin Prick Test

Widely-used test used to identify allergens responsible for triggering symptoms of type I hypersensitivity reactions. It is regarded as a safe method of investigating sensitization in children[15]. Different types of allergen will be exposed to the body through the skin. A wheal diameter $\geq 3\text{mm}$ will be considered positive.

Screening Questionnaire

To screen out healthy individuals and individuals with allergic rhinitis, a screening questionnaire adopted from ISAAC (International Study of Asthma and Allergies in Childhood) Core Manual and supplementary questionnaires on rhinitis and rhinitis management[16] with extra questions added according to ARIA (Allergic Rhinitis and its Impact on Asthma) classification. ISAAC and ARIA have been shown to be useful in evaluating prevalence and severity of allergic rhinitis in school children[17]. Baseline Total Nasal Symptom Score (TNSS)[18] will also be evaluated in the questionnaire (Appendix 3).

Treatment Diary

Subjects are required to fill in an 8-week diary for drug compliance monitoring (Appendix 5). Everyday subjects are required to fill in the time at which they took the medication and are given the opportunity to jot down additional remarks. This is to ensure treatment compliance, and not for the interpretation of treatment outcomes.

SUBJECTS AND METHOD

Subjects

Students aged 11 to 14 currently studying Form 1 and 2 in secondary school will be recruited directly through invitation. Recruitment will include patients suffering from untreated allergic rhinitis in addition to healthy individuals to serve as a control group. Patients suffering from allergic rhinitis will be classified according to ARIA guidelines into mild/moderate/severe, and duration into intermittent/persistent. Patients suffering from rhinitis due to non-allergic origins or those associated with nasal polyposis or sinusitis will be excluded. Patients are going to complete the Rhinitis Symptom Utility Index (RSUI) questionnaire for assessing pre and post symptoms.

Control Group- Inclusion Criteria

1. Both genders of 11-14 years
2. Chinese in ethnicity
3. Subjects who have not been diagnosed with a long term medical or psychiatric problem
4. Subjects who are not currently undergoing any long term medical treatment.

Patient Group- Inclusion Criteria

1. Both genders of 11-14 years, diagnosed with allergic rhinitis on basis of screening instruments, medical history, clinical assessment (by general ORL examination including nasal endoscopy)
2. Chinese in ethnicity
3. Positive skin prick test with wheal diameter $\geq 3\text{mm}$

4. Ability to understand the nature, scope, and possible consequences of the study
5. Capability and willingness to comply with the requirements of the protocol

Patient Group- Exclusion Criteria

1. Subjects with co-existing nasal conditions other than AR, which may affect nasal pathology (nasal polyposis, sinusitis, severe deviations of nasal septum, tumors of the nasal cavity, acute/chronic rhinosinusitis or any underlying pathology that might affect nasal breathing or nocturnal sleep)
2. Subjects with prior nasal surgery (e.g. nasal cavity, sinuses)
3. Subjects with known brain disorders, prior brain surgery or history of stroke
4. Subjects diagnosed with learning disability, autism or attention deficit hyperactivity disorder (ADHD)
5. Subjects with history of known sleep disorder, central or obstructive sleep apnea, narcolepsy, insomnia, patients requiring regular sleep medication and those hypersensitive to applied topical nasal steroids
6. Subjects who have taken topical nasal steroids, oral anti-histamines or medications affecting nasal symptoms 30 days prior to commencement of study
7. Subjects with hypersensitivity reactions towards topical nasal steroids or oral anti-histamines
8. Subjects previously diagnosed with any psychiatric disorders
9. Subjects who suffered from a respiratory tract infection within the past 30 days
10. Subjects who have clinically major cardiovascular, respiratory, hepatic, neurological, endocrine, immunological or other major systemic disease(s)
11. Subjects who are undergoing a long-term medical treatment plan

TREATMENT AND COMPLIANCE

Medication (complying with standard treatment guidelines) will be prescribed to the patient group. As this study does not investigate the efficacy of a specific drug, the medication plan will be up to the discretion of the attending physician with the aim of alleviating nasal symptoms. Commonly, pediatric allergic rhinitis treatment involves topical nasal steroids and 2nd generation antihistamines. Compliance will be monitored via the treatment diary, phone call after four weeks of treatment, and pill counting. Should issues arise anytime during the study, research staff will be available for subjects to contact during office hours. To increase the incentives of the participants, reinforcement programs, such as hospital visits and a health-related seminar, will be held. Each participant will receive a certificate upon completion.

METHOD OF ANALYSIS

Multilevel models, the mixed effects models [19], will be used to compare the longitudinal rate of change on cognitive function and different areas of cognitive function (as measured by Digit Span Test, Stroop Test, Chinese Auditory Verbal Learning Test, Verbal Fluency Test, and Trail Making Test) both within and between normal and allergic rhinitis patients. Multilevel models are random effects models that take into account the hierarchical nature of the data, and the within- and between-subject heterogeneity [20]. For longitudinal data, such models allow for measurements made at unequal intervals and with a varied number of measurements (i.e. subjects who may have one or several measurements). The models are fitted by the method of restricted iterative generalized least-squares algorithm of MLn for Windows software package, Version 2.0 (Institute of Education, University of London, London, UK). The likelihood ratio test is used to assess the statistical significance of the estimates at the 5% level. The model assumptions are checked by inspection of the standardized residuals for normality and constant variance.

PROPOSED TIMELINE

Week 0

- A. Consent will be sought from potential subjects
- B. Screening questionnaires (based on the ARIA and ISAAC questionnaires) will be given to the parents of the subjects as a preliminary assessment of the subject's condition
- C. Pre-treatment RSUI questionnaire will be given and explained to those suspected to suffer from allergic rhinitis.

Week 1

- A. Subjects who are suspected to suffer from allergic rhinitis will undergo a skin prick test to exclude the possibility of non-allergic rhinitis.
- B. Subjects who are suspected to suffer from allergic rhinitis will then be assessed by ENT specialist to perform screening of individual's eligibility for participation in the study on the basis of medical history, clinical assessment including general ORL exam and nasal endoscopy to exclude any physical obstructions in the nasal cavities that might affect nasal breathing or nocturnal sleep.
- C. Inclusion and exclusion criteria will be checked
- D. Patients diagnosed to suffer from allergic rhinitis will be prescribed a personalized medical treatment which is to begin when instructed 1 week later.

Week 2

- A. Subjects undergo cognitive testing (Digit Span Test, Stroop Test, Chinese Auditory Verbal Learning Test, Verbal Fluency Test, and Trail Making Test)
- B. Subjects are instructed to begin personalized medical treatment the day after cognitive testing.
- C. Patients are reminded not to use over-the-counter drugs or prescription medications that could affect rhinitis symptoms during the treatment period and to record any medications they take.

Week 6

Reminder calls to continue treatment plan and treatment diary to ensure compliance

Week 10

- A. End of treatment plan.
- B. All unused drugs will be collected to check for compliance
- C. Subjects undergo cognitive testing (Digit Span Test, Stroop Test, Chinese Auditory Verbal Learning Test, Verbal Fluency Test, and Trail Making Test)
- D. Subjects complete post-treatment RSUI questionnaire
- E. Subjects presented with completion certificate

REFERENCES

1. New Publication by HKU Paediatricians : 'Allergic Rhinitis – The Paediatric Disease You Must Learn' - All News - Media - HKU. (n.d.). Retrieved October 10, 2017, from http://www.hku.hk/press/news_detail_6527.html
2. Aetiology of allergic rhinitis in Hong Kong. (2015, March 19). Retrieved October 10, 2017, from <http://www.sciencedirect.com/science/article/pii/S1323893015315343>

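### The plan describes its school population in three ways and names no age or form term, so the patient-control level comparison is left unadjusted

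*Combined protocol and SAP*

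**What the plan says.** The combined protocol and SAP describes the population in three ways.

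- The Brief Summary has: "Pilot study on the association between allergic rhinitis and cognitive ability in children aged 11-14 within the same year group at school". This is one year group, with an age range of 11-14.
- Study Sample and Setting: "subjects aged 11-14 studying Form 1 and 2 in secondary school being recruited". Subjects, under Subjects and Method, agrees: "Students aged 11 to 14 currently studying Form 1 and 2 in secondary school will be recruited directly through invitation". This is two year groups with the same age range.
- Study Sample and Setting, on expected numbers: "The total number of the Form 1 students within the school will be around 200". With 70% participation and 24.5% prevalence, this leads to 140 participants and 34 patients. The Brief Summary gives the matching 106 controls. This is Form 1 only.

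The control criteria ask only for an age between 11 and 14, with no matching or frequency-matching on age or form. Method of Analysis compares the groups with multilevel models "both within and between normal and allergic rhinitis patients" and names no covariate or stratification factor. Objectives 1 and 2 concern how normal children and patients differ in cognitive function. Objective 3 and the hypothesis concern improvement over treatment.

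**The concern.** A comparison of patients with controls at one time point in a non-randomised study depends on who the controls are. The summary implies that schooling is held constant. The recruitment text does not, and the model contains nothing to restore it. Age is not held constant under any of the three descriptions, because each allows, or does not narrow, the 11-14 range.

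The outcomes include words recalled, words produced in one minute, response times and digit-series length, and no age-standardised scoring is described. If scores move with age or schooling over this range, two things follow for Objectives 1 and 2. A difference in age or form mix between patients and controls would be read as an effect of rhinitis. The spread of scores due to age would also stay in the error term and widen the interval.

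**Working it through.** **1. The plan's own count.** 200 x 0.70 = 140; 140 x 0.245 = 34.3, so 34 patients; 140 - 34 = 106 controls. The figures reproduce exactly, and the 200 are Form 1 students. The plan states no power, effect size or SD, so there is no power figure to reproduce.

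**2. Precision at those sizes.** The SE of a standardised level difference is sqrt(1/34 + 1/106) = 0.197 SD. For an assumed true difference of 0.5 SD and a two-sided 5% normal test, power = Phi(0.5/0.197 - 1.96) = 71.8%.

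**3. Adding an age term.** The documents give no correlation R between age and score, so a range is assumed. The residual SD becomes sqrt(1 - R^2), and power = Phi(0.5/(0.197 x sqrt(1 - R^2)) - 1.96).

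| Assumed R | Power | Gain (points) |
|---|---|---|
| 0.1 | 72.2% | 0.4 |
| 0.2 | 73.5% | 1.7 |
| 0.3 | 75.8% | 4.0 |
| 0.4 | 79.0% | 7.2 |
| 0.5 | 83.4% | 11.6 |

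**4. Adding a form term only.** Take an assumed gap g between forms, in within-form SD units, and an assumed even split. The unadjusted SD is sqrt(1 + g^2/4). With the 0.5 difference in within-form SD units, adjusted power is 71.8%. Unadjusted power is 71.7%, 71.4%, 70.8% and 69.2% for g = 0.1, 0.2, 0.3 and 0.5. The gain is 0.1 to 2.6 points.

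**5. Bias from form mix.** Bias = g x (difference in Form 2 share between the groups). By chance, with an even split, that difference has SD sqrt(0.25 x (1/34 + 1/106)) = 0.099, about 10 points. At 10 points and g = 0.3-0.5, bias is 0.03-0.05 SD. Given such an imbalance, a nominal 5% test rejects about 5.3-5.7% of the time under no effect. Reaching 0.15 SD (11.9%) needs g = 0.5 and a 30-point difference, which is about 3 chance SDs.

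**6. If both forms are recruited.** Assume Form 2 also has about 200 students. Then 400 x 0.70 = 280 participants, and 280 x 0.245 = 68.6, about 69 patients and 211 controls. SE = sqrt(1/69 + 1/211) = 0.139, and power at 0.5 SD is about 95%.

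**7. The change contrast.** An age or form effect that is constant over the 8 weeks cancels within a child measured twice. What remains is any practice gain that depends on age or form, and the between-child information that the model uses from children with only one measurement, whom Method of Analysis allows.

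**The case against.** The strongest reply is that nothing here shows bias. Both groups come from one school with one age range, no form split is given, and the plan offers no reason why rhinitis should follow form. A chance imbalance leaves the error rate at 5% on average. The hypothesis and the model's named target concern change, where a constant age or form effect cancels. The study is a pilot with no power target, and the relation of score to age is not in the documents. All of this stands, and it limits the size of the point.

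Three stronger readings are tempting but not supported.

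- *Recruiting two forms widens the age span.* The summary already gives 11-14, so only the form differs between sections.
- *Pooling two forms costs power.* The 34 and 106 come from Form 1 alone. If that count describes the sample, there is no form mix. If Form 2 is added, the sample may be larger and power higher (step 6).
- *The level contrast is confounded by form.* That needs a real difference in form mix and a gap between forms, and the documents show neither. Even that both forms will be pooled is unsettled.

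What the reply does not remove is the disagreement between sections, or the absence of an age term in a non-randomised, unmatched comparison. A covariate has to be named before any imbalance is seen; adding it afterwards is a data-driven choice. Method of Analysis lists no model terms in detail, so its silence does not rule out adjustment, but neither does it commit the analysis to one.

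**Conclusion.** The point holds in a limited form. The sections on population must be reconciled, and the level contrast for Objectives 1 and 2 is unadjusted for age (and for form, if both forms are recruited). The age part applies whichever population is intended.

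The likely cost is modest: 0.4 to 4.0 power points for an age correlation of 0.1-0.3, more only if the correlation is 0.4 or higher, and under 3 points for form alone. A typical chance form imbalance would shift the contrast by 0.03-0.05 SD. These sizes assume a 0.5 SD true difference, the stated ranges for the age correlation and form gap, an even form split and the plan's 34 v 106. None of these except the group sizes comes from the documents. This is a nearly free improvement to Objectives 1 and 2, and it does not threaten the change hypothesis.

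**What to change.** 1. State one population, in the same terms, in the Brief Summary, Study Sample and Setting, and Subjects. If Form 2 is included, redo the expected numbers from the enrolment of both forms.
2. In Method of Analysis, prespecify age at Week 2 as a fixed effect in the multilevel model for each test. If both forms are recruited, add form and form-by-time; with Form 1 only, these terms cannot be estimated and should be left out.
3. State that the patient-control contrasts for Objectives 1 and 2 are taken from that model.

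The cost is wording, plus a short recalculation if Form 2 is in. Age is needed for eligibility and form is known at recruitment, so no new data are required. Each model gains one to three parameters, with about 140 children on the plan's own count.

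### Five cognitive tests are primary under one hypothesis and judged at 5% with no multiplicity control or success rule; if any one counts, the chance of a false positive is 18–23%, or 9–12% in the patients' favour

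*Combined protocol and SAP*

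**What the plan says.** BRIEF SUMMARY OF STUDY lists the primary outcomes without ranking them: "Primary outcome measures include cognitive tests (Digit Span Test, Stroop Test, Chinese Auditory Verbal Learning Test, Verbal Fluency Test, and Trail Making Test". RESEARCH HYPOTHESIS makes one directional statement: "Children with allergic rhinitis are expected to have a heightened improvement in cognitive abilities after the treatment compared to the normal control group". It names no test and no number of tests. RESEARCH OBJECTIVES also asks a question by area: "To investigate the impact of allergic rhinitis on different areas of cognitive function".

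METHOD OF ANALYSIS specifies multilevel models for change in cognitive function and its different areas, within and between groups. It adds: "The likelihood ratio test is used to assess the statistical significance of the estimates at the 5% level". The document contains no multiplicity adjustment, hierarchy, composite, global test or success rule.

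MATERIALS AND INVESTIGATIONS USED describes the scores:

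- **Digit Span:** "There are two parts of the test: forward span and backward span". The two parts are said to measure different abilities, and neither is chosen for analysis.
- **Stroop:** three card times are recorded. Interference is to come from time differences, but the cards to be contrasted are not named.
- **Auditory Verbal Learning:** five learning recalls of List A, a List B recall, a List A recall after interference, a 30-minute delayed recall, and recognition. The text says: "The number of words recalled will be used as a measurement of memory retrieval".
- **Verbal Fluency:** "The number of words spontaneously produced within 1 minute will be measured".
- **Trail Making:** two sheets, with no analysis score named.

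**The concern.** Several unranked primary outcomes sit under one hypothesis, and the plan does not say which pattern of results would support it. One positive test out of five and five out of five are both compatible with the text, yet they are very different standards of evidence. If a single positive test were taken as support, a chance result on one of the five could be presented as better cognition in treated patients. Open scoring adds to this, because the number of comparisons is itself not fixed.

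**Working it through.** **Plan's own figure.** STUDY SAMPLE AND SETTING gives about 200 students, 70% participation and 24.5% prevalence. 200 × 0.70 = 140; 140 × 0.245 = 34.3, so 34 patients; 140 − 34 = 106 controls. These match the plan. They are a recruitment forecast, not a power calculation, and they do not drive the false-positive rates below. The plan states no error rate for the five tests together.

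**Inputs from the plan.** Five primary tests, each at 5%. Sidedness is not stated; a likelihood ratio test of one coefficient is two-sided, so 2.5% falls in each direction.

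**Assumptions.** No true effect; one group-by-time contrast per score; any one significant score counts; equal correlation ρ between test statistics. The plan gives no ρ, so a range is shown.

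**Formula.** At ρ = 0 with m scores, P(any) = 1 − 0.95^m and P(any favouring patients) = 1 − 0.975^m. For m = 5 these are 1 − 0.95^5 = 22.6% and 1 − 0.975^5 = 11.9%. For ρ > 0, equicorrelated normal statistics were integrated numerically with critical value 1.96. Each cell shows any false positive / one favouring patients.

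| ρ | 5 scores | 7 scores | 10 scores |
|---|---|---|---|
| 0 | 22.6% / 11.9% | 30.2% / 16.2% | 40.1% / 22.4% |
| 0.3 | 20.9% / 10.5% | 27.1% / 13.7% | 35.1% / 17.8% |
| 0.5 | 18.3% / 9.1% | 23.0% / 11.5% | 28.7% / 14.4% |
| 0.7 | 14.8% / 7.4% | 17.8% / 8.9% | 21.3% / 10.7% |

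Seven scores means both parts of Digit Span and of Trail Making are analysed. It is not an upper bound, because Stroop and Auditory Verbal Learning can also yield several scores. Ten is an illustration.

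**Check.** Simulated t-tests on change scores at 34 v 106, five scores, 40,000 studies per ρ, gave 22.5% / 11.9% at ρ = 0 and 18.3% / 9.4% at ρ = 0.5.

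**Opposite rule.** If all five tests had to be significant in the patients' favour, the chance is below 0.01% at ρ = 0 and 0.3, 0.04% at 0.5, 0.21% at 0.7, 0.4% at 0.8 and 0.8% at 0.9.

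**Under Holm.** With no true effect, the first step (0.05 / 5 = 1%) sets the chance of any false positive. For five scores it is 4.9% / 2.5% at ρ = 0, 4.2% / 2.1% at 0.5 and 3.5% / 1.7% at 0.7.

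**Cost in power.** Detectable difference in baseline SDs = (z + 0.842) × √(2(1 − r)) × √(1/34 + 1/106). The last factor is 0.197, and r is the within-child correlation (assumed). The ratio of 1% to 5% is (2.576 + 0.842) / (1.960 + 0.842) = 1.22. With r = 0.7 the difference rises from 0.43 to 0.52; with r = 0.5, from 0.55 to 0.67; with r = 0.8, from 0.35 to 0.43. An effect with 80% power at 5% has Φ(2.802 − 2.576) = 59% at 1%.

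**The case against.** **It is a pilot.** "This study is a prospective longitudinal pilot study to take place from 1 Dec 2017 to 31 Dec 2018". There is no power calculation, and formal error control is often not expected of such a study. This stands as a reason for lower severity. It does not remove the gap, because the plan still pairs a directional hypothesis with a 5% significance rule.

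**Areas are separate questions.** The second objective asks about different areas, and separate results by test answer it. If conclusions are drawn strictly area by area, adjustment is a matter of judgement. What remains open is the single hypothesis about cognitive abilities as a whole.

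**Five separate tests is an assumption.** METHOD OF ANALYSIS refers to overall cognitive function as well as its areas and does not say one model per test. A joint analysis is not excluded, but none is defined.

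**Readers can correct for themselves.** All five tests are named in advance, so if all five p-values are reported a reader can apply any correction. That is fair, but it depends on full reporting and on one fixed score per test.

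**Stronger readings to avoid.** A reader might infer that the plan accepts one positive test as success, so that its error rate simply is 23%. The document neither says nor excludes that. A reader might also infer that the Stroop and Auditory Verbal Learning scores are settled. The sentence on words recalled follows the 30-minute recall, which makes that reading plausible, but the other counts are not ruled out and the Stroop contrast is unstated.

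**Conclusion.** The concern holds in conditional form. The plan has five unranked primary tests, one directional hypothesis, a 5% rule, and no statement of what counts as support. If any one test suffices, with one contrast per test and no true effect, the chance is 18–23% of some false positive and 9–12% of one in the patients' favour, for assumed correlations of 0.5 to 0. Both figures fall with higher correlation and rise with more scores; ten scores give 29–40% for any false positive over the same correlation range. Requiring all five would instead give 0.2% or less, but only up to a correlation of about 0.7. The unstated rule therefore largely determines the error rate. Severity is minor to should-fix, given the pilot design.

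**What to change.** Add to METHOD OF ANALYSIS:

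1. Name one analysis score for each of the five tests. The sponsor chooses the Digit Span and Trail Making scores, states which Stroop cards are contrasted, says which Auditory Verbal Learning count is used, and confirms the one-minute fluency count.
2. Test the five between-group group-by-time effects with Holm at an overall two-sided 5%: ordered p-values against 1%, 1.25%, 1.67%, 2.5% and 5%, stopping at the first failure.
3. Report all five effects with 95% confidence intervals, including any unfavourable result.
4. Limit claims to the specific tests that are Holm-significant, and word them as associations because the groups are not randomised. State that one significant test supports improvement in that area only, not in cognitive abilities overall.
5. Label baseline group comparisons, within-group changes and other sub-scores descriptive, or apply Holm to the baseline family as well.

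**Alternative for a pilot.** Drop the 5% rule and report all five effects as exploratory with confidence intervals. This avoids the loss of power.

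**Cost.** Wording only, with no new data. Holm's strictest step raises the detectable difference by 22% and takes 80% power down to 59%. The rule must be set before outcome data are examined. This version is dated 11 April 2018, after the study window opened on 1 December 2017, so the sponsor should confirm that the data were unexamined or label the rule post hoc.
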